The clinical manifestation of CN is unexplained unilateral inflammation of the foot and/or ankle with or without pain. If there has been a delay in the patient seeking medical advice deformity may already be present¹². The aim of treatment is to stop the inflammatory process, relieve pain and maintain foot architecture¹³. The international consensus is that the foot should be immobilised in a non-removable device with weekly or fortnightly review¹⁴. This immobilises the foot, minimising the potential for any further damage. Immobilisation is continued until resolution/remission, this is when there are no longer clinical signs of inflammation, and x-rays are stable with signs of consolidation¹⁵.

Late diagnosis or inadequate off-loading can lead to significant foot deformity, which is the precursor of foot ulceration. An observational study from the USA showed that delayed referral by primary care practitioners to secondary care was associated with a higher chance of CN progressing and subsequent complications developing¹⁶. Another observational study reported ulceration rates of 37%. 6% of patients developed ulceration during the acute phase of CN, and 31% when the CN

was chronic as a result of footwear design issues, delayed delivery of footwear or patient compliance with wearing the footwear¹⁷. Ulceration on a CN foot is extremely difficult to heal, the situation is further complicated when infection develops increasing the risk of amputation. Annual major amputation rates for CN vary between centres from 2.7%- 6.6%^{18,19}. In many cases, people can no longer provide for themselves or their families. Only 50% of patients who have had a major amputation survive for a further two years²⁰. Mortality is increased; average life expectancy is reduced by 14.4 years compared to the general UK population²¹

Studies from the UK have demonstrated a median time to remission of between 9-12 months^{9,22,23}. However studies from the USA demonstrate considerably shorter immobilisation times between 3-5 months²⁴⁻²⁷. Results from Brazil and Germany show remission times of 3-12 months and 3-6 months respectively^{28,29}. Such a prolonged period of immobilisation is a source of enormous social limitation and consequent reduction in quality of life for the patient³⁰. The literature suggests the duration of immobilisation may be influenced by the anatomical location of the CN and the stage of CN when immobilisation is initiated³¹.

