6.4 Interventions - Arm A and Arm B

All patients will attend the secondary care clinic for fortnightly visits or as per current standard care, outlined in 6.4.5. Additional visits maybe arranged depending on clinical need. Procedures which are part of standard care will be completed according to trial specific WPD.

In this trial a standardised assessment of serial temperature measurements will be carried out. This will be completed according to trial WPD. The temperature of both feet will be recorded at intervals of 5 minutes starting at the initial removal of the off-loading device for up to 15 minutes. This will assess acclimatisation and the period of equilibration needed for stabilisation of temperature.

- 1) Following initial removal of the off-loading device
- 2) Following a 5 minute resting period
- 3) Following a 10 minutes resting period
- 4) Following a 15 minutes resting period

The sites where the temperature will be recorded reflect the current classification tool developed by Sanders and Frykberg⁴⁸;

1. distal and proximal interphalangeal joints, metatarsophalangeal, tarsometatarsal joints
2. naviculo-cunieform joints, talo-navicular joint
3. calcaneocuboid joint
4. ankle joint, subtalar joint
5. calcaneus

One X-ray will be additional to standard care this will be taken 6 months post remission. Participants who do not reach this time point within the 18 month intervention and follow-up period will not have this X-ray. This will enable the progression of foot deformity to be assessed. If a participant becomes pregnant during the study they will not have the additional X-ray and will be excluded from the analysis of the progression of foot deformity. Two members of the research team will independently evaluate the images to assess the progression of foot deformity. Inter-rater reliability will be assessed. The X-rays will be anonymised prior to evaluation to ensure the researcher is blinded to participant number and site. [The anonymised scans will also be randomly sequenced to avoid bias.](#)

To allow comparison all X-ray and MRI images will be taken as per trial WPD.

The participants will also be asked to complete the following questionnaire/assessments. These will be completed at randomisation, 3 monthly until remission (3, 6, 9 and 12 months), 1 month after remission, and at 6 months post remission;

- 1) Pain in the foot and/or leg measured using a numerical 0-10 visual analogue scale

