6.4.2 Arm B (Control – Standard Care and one additional MRI)

Immobilisation discontinued on the basis of clinical remission determined by skin temperature measurement and MRI. In the standard care arm participants will receive one additional MRI when the temperature measurements, X-ray and/or signs and symptoms indicate to the clinical team that the foot is in remission.

A temperature difference of $\leq 2^{\circ}\text{C}$ which is maintained or improves on two separate consecutive occasions for a period of ≥ 4 weeks will be the indicator to arrange the second MRI, to confirm the diagnosis of remission.

If participants in either arm of the trial have not reached remission at the end of the 12 month active phase of the study they will exit the study. Ongoing standard care will be provided by their clinical team.

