6.5.2 Exploratory Clinical Outcomes

- Days with immobilisation, measured at the end study
- Progression of foot deformity as documented by measuring radiological foot alignment angles. All x-rays will be taken in a weight bearing position with standard views as per WPD. Comparison from baseline, diagnosis of remission, and six months after remission. The angles that will be assessed are:
 - Calcaneal Inclination – the angle formed by the horizontal and a line from the base of the heel and inferior cortex of the calcaneus
 - Talar Declination – the angle between the line originating from the centre of the talus bisecting the talar neck and head and the weight bearing plantar surface from the calcaneus to the 5th metatarsal
 - Talo-first metatarsal angle – the angle between the line originating from the centre of the talus bisecting the talar neck and head, and the line through the longitudinal axis of the first metatarsal.

- Hindfoot-forefoot angle - the angle between the talocalcaneal bisector and the second metatarsal shaft
- Cuboid height (mm) - the distance from the plantar aspect of the cuboid to a horizontal line drawn from the plantar calcaneal tuberosity to the fifth metatarsal head.

Patients who have undergone previous minor amputation and/or previous orthopaedic surgical fixation of the foot altering/removing the anatomical landmarks of the foot will be excluded from this analysis due to the absence of bony landmarks.

At each study visits the following will be measured and recorded on the eCRF:

- Number of new ulcerations on the index foot
- Number of new ulcerations on the contralateral foot
- Number of new infections on the index foot
- Number of new infections on the contralateral foot
- Number and severity of falls (Hopkins Fall Grading System)¹
- Number of minor and major amputations on the index foot at the end of the follow up phase of the study
- Number of minor and major amputations on the contralateral foot at the end of the follow up phase of the study
- The number of participants in each arm requiring further intervention for CN (e.g. further immobilisation) within 6 months of remission

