6.7.2 The “active phase” – up to 12 months

These visits will take place in the participant’s usual place of care (secondary care). Participants will attend for fortnightly visits. Standard care and study specific procedures will be carried out and recorded on the eCRF.

Study Specific Procedures

- The temperature assessment as per the WPD
- The participant diary will be collected and another issued for participants to complete over the next 2 weeks, until their next study visit.

In both arms remission will be defined as an absence of sub-chondral bone marrow oedema on MRI, as reported by a specialist musculoskeletal radiologist and/or the absence of clinical signs and symptoms of CN. The clinical team will interpret the results of the MRI report to determine remission. As per standard care at this point patients will have a foot and ankle X-ray.

Participants who develop bilateral CN during the study can continue in the trial. The trigger to arrange the MRI in the standard care arm will be based on the absence of signs and symptoms of active CN as assessed by the clinical team.

Patients randomised to A (Intervention – Serial MRI)

Patients randomised to the intervention group will have an MRI of their foot and ankle three monthly (at 3, 6, 9 and 12 months) until the CN has settled. Where possible the scan should be scheduled to coincide with study visits to minimise the number of additional hospital visits.

For participants in the intervention arm if the MRI report indicates to the clinical team that the CN is not in remission participants will continue in the active phase of the study, up to a maximum of 12 months.

Patients randomised to B (Standard Care)

Patients randomised to the standard care will undergo an MRI once the temperature difference between their feet is $\leq 2^{\circ}\text{C}$ on two separate occasions at least four weeks apart.

For participants in the standard care arm if the MRI report indicates to the clinical team that the CN is not in remission participants off-loading will be recommenced. Participants will continue in the follow up phase as per the trial protocol.

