6.11 Data Collection, Management and Analysis

6.11.1 Data Collection Methods

Each participant will be given a unique trial Participant Identification Number (PIN), this will consist of the centre number and participant number (sequential). Data will be collected at the time-points indicated in the Trial Schedule (section 6.6).

The method of data collection is direct online entry of data onto the central database, stored on servers based at NCTU. This will be carried out by members of the trial team working within each research site. Data may be entered onto paper Case Record Forms (CRFs) prior to entry onto the database (but this is not an essential step). Staff will receive training on data collection and use of the online system.

X-ray images taken at baseline, remission and six month follow up will be transferred from site to the sponsor for analysis using the NHS Image Exchange Portal (IEP) or discs. All images will be anonymised by the site prior to transfer.

Data collection, data entry and queries raised by a member of the CADOM trial team will be conducted in line with the NCTU and trial specific Data Management Standard Operating Procedure.

Identification logs, screening logs, enrolment logs and tapes of qualitative interviews will be kept at the trial site in a locked cabinet within a secured room.

Clinical trial team members will receive trial protocol training. All data will be handled in accordance with the Data Protection Act 1998.

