6.11.4.2 Study Outcomes

Feasibility measures

- Number of eligible patients recruited, recruitment and retention levels, willingness of clinicians to participate in the study, and dropout rates.

Efficacy outcomes

- Days with immobilisation, for the intervention versus standard care will be measured
- Number of foot ulcers, infections, falls, minor and major amputations from randomisation to the end of the study
- Progression of foot deformity from randomisation – remission, and at the end of the study.
- Changes in psychological health status assessed by the Hospital Anxiety and Depression Scale (HADS) from baseline at, 3, 6, 9 and 12 months, remission and at the end of the study period.
- Changes in health related quality of life assessed by the Medical Outcomes Short-Form Health Questionnaire (SF12) from baseline at, 3, 6, 9 and 12 months, remission and at the end of the study period.
- Changes in reported pain experienced in the foot, ankle or leg as reported on a Visual Analogue Scale (VAS) from baseline at, 3, 6, 9 and 12 months, remission and at the end of the study period.

Economic Evaluation of resource use

- Collected through a patient diary

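### Every post-baseline X-ray named for foot deformity is tied to remission, so participants who exit at month 12 without remission generally drop out of a comparison labelled intention-to-treat

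*Protocol*

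**What the plan says.** The deformity outcome is set out in several places in the protocol.

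- **6.5.2** fixes the time points: "Comparison from baseline, diagnosis of remission, and six months after remission".
- **6.7.2** places the second film at the determination of remission: "As per standard care at this point patients will have a foot and ankle X-ray".
- **6.4** makes the third film the only X-ray beyond standard care, six months after remission, and adds: "Participants who do not reach this time point within the 18 month intervention and follow-up period will not have this X-ray". The timeline in 6.6 shows a study-specific X-ray at that visit and nowhere else.
- **6.11.1** limits what is read: "X-ray images taken at baseline, remission and six month follow up will be transferred from site to the sponsor for analysis".
- **6.4.2** states, for both arms, that participants who "have not reached remission at the end of the 12 month active phase of the study they will exit the study".
- **6.11.4.2** describes the outcome differently: "Progression of foot deformity from randomisation – remission, and at the end of the study".
- **6.11.5** says the exploratory efficacy analyses use the intention-to-treat population, on complete cases and without imputation.

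**The concern.** A participant who has not remitted by month 12 has a baseline film and, as a rule, nothing to compare it with. For this outcome a complete case is in practice someone who remitted. Earlier recognition of remission is what serial MRI is meant to achieve, so the intervention may change who is scored. If the arms remit at different rates, the scored participants are selected differently in each arm, and their contrast is not a comparison of the groups as randomised.

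Deformity is the structural consequence one would want to examine when the length of immobilisation changes, and section 5.1 calls it the precursor of ulceration. Feet that stay active for a year are plausibly among those most likely to deform, though the protocol gives no figure on this. The standard deviation passed to the definitive trial would also describe remitters only. Days with immobilisation is less exposed, because the Cox model in 6.11.4.1 can censor non-remitters, and ulcers, infections and falls are recorded at each visit.

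**Working it through.** The protocol states no proportion unremitted at month 12 and has no power calculation, so there is no printed figure to reproduce.

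**Step 1: who has a post-baseline film.** Following one participant through the text:

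| Participant | Remission film (6.7.2) | Six-month film (6.4, 6.6) | Sent for reading (6.11.1) |
|---|---|---|---|
| Remits by month 12 | yes | yes, if reached within 18 months | baseline and both later films |
| Not in remission at month 12, exits (6.4.2) | none planned | none planned | baseline only |

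The end-of-study value in 6.11.4.2 has no scheduled film for the second row.

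**Step 2: how many might be in the second row.** Inputs: "Studies from the UK have demonstrated a median time to remission of between 9-12 months" (5.1), and 60 participants, 30 per arm (6.8). Assumption: time to remission follows a Weibull curve with median m and shape k, where k = 1 is exponential. The proportion unremitted at month 12 is

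S(12) = 0.5^((12/m)^k).

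- m = 12: S = 0.5^1 = 50.0% for any k, or 30 of 60.
- m = 9, k = 1: 0.5^1.333 = 39.7%, or 23.8 of 60.
- m = 9, other shapes: k = 0.75 gives 42%; k = 1.5 gives 34%; k = 2 gives 29%; k = 3 gives 19% (11.6 of 60).

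So the UK medians give about 19% to 50%, and 40% to 50% if exponential. Section 5.1 also reports that "studies from the USA demonstrate considerably shorter immobilisation times between 3-5 months". Read as exponential medians, these give 0.5^(12/3) = 6% to 0.5^(12/5) = 19%.

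**Step 3: whether the loss would differ by arm.** UK figures describe past practice and apply most directly to Arm B. Assume a hazard ratio for remission of 1.5 to 2 in favour of Arm A (not in the protocol). Exponential curves then give S_A = S_B^HR:

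- m = 9: Arm B 39.7% (11.9 of 30); Arm A 25% (7.5) at 1.5 and 16% (4.7) at 2.
- m = 12: Arm B 50% (15 of 30); Arm A 35% (10.6) at 1.5 and 25% (7.5) at 2.

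**Step 4: illustrative bias only.** Suppose slow remission and worse deformity have correlation 0.3 to 0.5, with 50% remitting in Arm B and 70% in Arm A. None of these values is in the protocol. The mean of the fastest 50% of a standard normal is -0.80, and of the fastest 70% is -0.50. Multiplying by the correlation, Arm B's mean deformity is understated by 0.24 to 0.40 SD and Arm A's by 0.15 to 0.25 SD. With no true effect, the scored groups would differ by 0.09 to 0.15 SD, to the apparent disadvantage of Arm A. With 15 and 21 scored, the standard error of the difference is sqrt(1/15 + 1/21) = 0.34 SD, so a bias of this size would be well inside the noise of this trial.

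**The case against.** The strongest defence has four parts.

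- **The outcome is exploratory.** It is one of many in an unpowered feasibility trial, and 6.11.4.1 says so. This stands. The harm is to interpretation and to the estimates handed on, not to a confirmatory test.
- **The analysis plan could supply labels and counts of missing films.** This stands in part. But no analysis plan can recover films that 6.11.1 does not have transferred, and the conflict between 6.11.4.2 and the other sections lies in the protocol itself.
- **A reader might infer that a non-remitter can never be scored.** The text does not go that far. Section 6.7.2 defines remission by MRI and/or absence of clinical signs, and says Arm B participants whose MRI does not show remission carry on in follow-up. A few without MRI remission might therefore be filmed. That wording does not help those who exit at month 12.
- **A reader might take 40% to 50% as the protocol's own figure, or count amputation on the index foot as a further route out.** Neither is supported. The protocol prints only medians, and the lower end of that range needs a constant remission rate. Amputations are recorded as outcomes, and no section makes them an exit. An alternative diagnosis is an exit (6.7.5), but those participants are judged not to have the disease, so it is a different kind of loss.

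It is also fair to say that the protocol does not show that routine films between baseline and remission exist, or that they would meet the required views. The fix must be conditional on that.

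**Conclusion.** The structural point holds and does not depend on any percentage. All post-baseline films named for deformity hang on remission, participants unremitted at month 12 exit in either arm, and the end-of-study time point and the intention-to-treat label cannot be met for them. The plan as written compares groups selected by an event after randomisation that the intervention aims to change.

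The size is uncertain. On the UK medians roughly 20% to 50% would be unremitted at month 12, before withdrawals and other exclusions. The 50% end follows from the 12-month median alone, and the lower end depends on curve shape. The share is smaller if remission is faster, as in the USA times or if serial MRI works as intended. The bias in SD units only illustrates the direction under unsourced assumptions and should not be cited as an estimate. This should be corrected, but for an exploratory outcome it does not threaten the trial's main feasibility aims.

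**What to change.** In 6.5.2, 6.11.1 and 6.11.4.2:

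1. State that, for a participant who exits without remission, the last film of the index foot already taken in routine care before exit is transferred, provided that one exists and meets the weight-bearing views in the trial's working practice document. It is read with the others and analysed with its time since randomisation.
2. Report by arm how many participants have no post-baseline film, and why.
3. Reconcile the end-of-study time point in 6.11.4.2 with 6.4, 6.4.2, 6.5.2 and 6.11.1.
4. State that contrasts at remission and six months later are descriptive among remitters and are not intention-to-treat effects. Label the variability estimates for the definitive trial in the same way.

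The cost is wording, plus transfer and reading of existing films; no X-ray is added. The drawback is that film timing will vary and some non-remitters may have no usable film. The count in item 2 would then itself be useful feasibility information.

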6.4.6 Protocol Treatment Discontinuation

In consenting to the trial, participants are consenting to trial treatments, trial follow-up and data collection. However, an individual participant may stop treatment early or be stopped early for any of the following reasons:

- Adverse event which in the opinion of the treating clinician makes them unsuitable for continued participation in the study
- Inter-current illness that prevents further treatment

- Any change in the participant's condition that in the clinician's opinion justifies the discontinuation of treatment
- Participants who become pregnant during the trial can continue in the trial. They will be excluded from the final X-ray at 6 months post remission.
- Withdrawal of consent for treatment by the participant
- Participant who moves away from the area or decides to transfer to a different hospital for the management of their CN.

As participation in the trial is entirely voluntary, the participant may choose to discontinue trial treatment at any time without penalty or loss of benefits to which they would otherwise be entitled. Although not obliged to give a reason for discontinuing their trial treatment, a reasonable effort should be made to establish this reason, whilst remaining fully respectful of the participant's rights.

Participants who discontinue protocol treatment, for any of the above reasons, should remain in the trial for the purpose of follow up and data analysis.

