6.12.3.2 Procedures to follow in the event of female participants becoming pregnant

In the event of a female participant becoming pregnant they have the option to withdraw from the trial. All participants who become pregnant will be excluded from the X-ray at 6 months post remission.

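### The foot-deformity analysis excludes whole participants for altered landmarks or pregnancy, where the reasons given reach only particular measures or one time point

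*Protocol*

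**What the plan says.** Progression of foot deformity is an exploratory clinical outcome, measured on X-ray by four angles and cuboid height (Protocol 6.5.2). The comparison is described as "Comparison from baseline, diagnosis of remission, and six months after remission", and the statistical section lists it as "Progression of foot deformity from randomisation – remission, and at the end of the study" (6.11.4.2).

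Two rules remove participants from it:

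- **Previous surgery (6.5.2).** The rule applies to anyone with "previous minor amputation and/or previous orthopaedic surgical fixation of the foot altering/removing the anatomical landmarks of the foot". The consequence is set for the patient as a whole: such patients "will be excluded from this analysis due to the absence of bony landmarks". Nothing is said about analysing the measures whose landmarks are intact.
- **Pregnancy (6.4).** If a participant becomes pregnant, "they will not have the additional X-ray and will be excluded from the analysis of the progression of foot deformity".

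Two other sections deal with pregnancy and go less far. Section 6.4.6 says "They will be excluded from the final X-ray at 6 months post remission", and 6.12.3.2 says "All participants who become pregnant will be excluded from the X-ray at 6 months post remission". Neither mentions removal from an analysis. Section 6.11.5 puts the exploratory efficacy analyses on an intention-to-treat, complete-case basis without imputation.

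**The concern.** A missing landmark makes a particular measurement impossible; it does not make a participant unmeasurable. A missing 6-month X-ray removes the comparisons that use that X-ray, and leaves the baseline-to-remission change intact if both of those films exist. Both rules nevertheless act on the whole participant, so they discard readings that the protocol's own definitions and schedule make valid.

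The surgical rule is also open to two readings. The words about altering or removing landmarks follow fixation directly and may or may not reach back to amputation, so two analysts could build different analysis sets from the same sentence. The pregnancy rule is wider in 6.4 than in the two other places where the subject is handled, and it depends on an event after randomisation.

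At stake is usable data on one exploratory outcome in a trial limited to 60 participants. Estimating the variability of key outcomes for a definitive trial is one of its stated purposes (6.5.1, 6.11.4.1), and deformity is read by two evaluators from anonymised, randomly sequenced images (6.4) in an otherwise open trial.

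**Working it through.** The protocol gives no figure for either exclusion and no power calculation (6.8), so there is nothing to reproduce. The check has three parts.

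**1. Which bones each measure needs (definitions in 6.5.2)**

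| Measure | Bones used |
|---|---|
| Calcaneal inclination | calcaneus |
| Talar declination | talus, calcaneus, 5th metatarsal |
| Talo-first metatarsal angle | talus, 1st metatarsal |
| Hindfoot-forefoot angle | talus, calcaneus, 2nd metatarsal |
| Cuboid height | cuboid, calcaneus, 5th metatarsal |

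Striking out each measure that needs a lost or altered bone leaves:

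| Situation | Measures left of 5 |
|---|---|
| Toe only, or ray 3 or 4 only | 5 |
| Ray 1 only, or ray 2 only | 4 |
| Cuboid altered | 4 |
| Ray 5 only | 3 |
| Rays 1 and 2 | 3 |
| Rays 1 and 5 | 2 |
| All rays | 1 |
| Talus altered | 2 |
| Calcaneus altered | 1 |
| Talus and calcaneus altered | 0 |

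If the qualifier does not cover amputation, the first row is excluded with all five measures obtainable. If it does, the participant-level rule still discards 3 or 4 valid measures after loss of ray 1, 2 or 5 alone.

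**2. Size of the loss from the surgical rule**

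Inputs: 60 participants (6.8) and five measures (6.5.2), giving 60 × 5 = 300 participant-measures per comparison. The share with excluding surgery is not given; 10% to 25% is assumed, which is 6 to 15 participants.

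- At 10%, the current rule loses 6 × 5 = 30 of 300. A per-measure rule would lose 6 × 1 = 6 if all six had lost ray 1 or ray 2, 6 × 2 = 12 if all had lost ray 5, and 6 × 4 = 24 if all had lost every ray.
- Interval width varies as 1/√n. Width with all kept, relative to width with the exclusion, is √(54/60) = 0.95 at 10% and √(45/60) = 0.87 at 25%. The interval is therefore about 5% to 13% narrower for a measure that none of the affected participants has lost.
- In SD units, the 95% half-width of a difference between two equal arms is 1.96 × √(4/n): 0.51 at n = 60, 0.53 at n = 54 and 0.58 at n = 45.
- For the SD itself, with n − 2 degrees of freedom, the 95% limits as multiples of the estimate are √(df/χ²) at the 97.5% and 2.5% points: 0.85 to 1.22 at n = 60, 0.84 to 1.24 at n = 54 and 0.83 to 1.27 at n = 45.

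The 5-13% is an upper limit, because any affected participant who has lost the measure in question adds nothing to it. The half-widths assume that all 60 are otherwise evaluable, which is the best case: participants not in remission at 12 months leave the study (6.4.2), as do those given another diagnosis (6.7.5).

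**3. The pregnancy passages side by side**

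- 6.4: no 6-month X-ray, and out of the deformity analysis.
- 6.4.6 and 6.12.3.2: no 6-month X-ray; nothing about the analysis.
- 6.5.2 and 6.11.4.2: change from baseline (randomisation) to remission is a planned comparison. It does not use the 6-month film, and the remission X-ray is standard care (6.7.2).
- 6.4 again: participants who do not reach 6 months post remission within the study period simply lack that X-ray, with no exclusion stated. The same missing film is thus handled in two ways within one section.
- 6.11.5: intention-to-treat. Removing a participant from every comparison because of an event after randomisation, when a planned comparison can still be computed, does not fit that statement.

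**The case against.** The strongest reply on surgery is that the qualifier already limits the rule. Since the stated reason is missing landmarks, the natural reading is that a toe amputation leaving every landmark in place is not excluded. That reading is fair, but the sentence does not settle it, and even on that reading a lost first metatarsal takes four other measures with it.

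On pregnancy, 6.4 introduces the 6-month X-ray as the means of assessing deformity and then excludes pregnant participants, so it may intend only the analysis that this film makes possible. If so, the sections can be reconciled, but the words of 6.4 name the deformity analysis without that limit. The protocol also does not say whether a participant who is pregnant before remission has the remission X-ray, so the baseline-to-remission change is not guaranteed to exist.

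One can add that a common analysis set across five measures is a legitimate choice, and that evaluability codes belong in a statistical analysis plan. The codes do; the exclusions themselves are fixed in the protocol.

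A reader might go further and infer three things that the documents do not support:

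- *That most of the five measures always survive.* Only 1 to 3 remain in the multi-ray situations tabulated, and 0 to 2 after talar or calcaneal alteration.
- *That the rule removes the feet most likely to progress and so biases the planning figures.* Nothing in the protocol links previous minor amputation to progression, and the suggested primary efficacy outcome is days with immobilisation (6.11.4.1).
- *That the surgical exclusion biases the comparison of arms.* It rests on previous surgery, a status fixed before randomisation.

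**Conclusion.** The point holds as a low-severity improvement. Section 6.5.2 excludes by participant for a reason that applies by measure, and leaves the reach of its qualifier unclear. Section 6.4 excludes a participant who becomes pregnant from more than 6.4.6 and 6.12.3.2 imply, after randomisation and out of step with 6.11.5.

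The cost is some precision and generalisability on one exploratory outcome in an unpowered feasibility trial. On an assumed 10-25% with excluding surgery, the gain is at most about 5-13% in interval width for measures unaffected in those participants, and less for the others. The number of pregnancies is not given and no size is put on that part; its weight lies in the inconsistency. The counts of surviving measures rest only on the bones named in the five definitions.

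**What to change.** - **6.5.2:** replace the participant-level exclusion with wording such as: *A measurement is omitted only where a landmark it requires is absent or altered on that X-ray; the participant's other measurements and time points are analysed.* This applies equally to amputation and fixation, so the question of what the qualifier covers no longer arises.
- **6.4:** reconcile the analysis-set wording with 6.4.6 and 6.12.3.2, so that any planned comparison for which both X-rays are available is analysed. Whether a pregnant participant is imaged is a clinical matter and is not addressed here.
- **Reporting:** give the number evaluable for each measure in each arm.

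The cost is two sentences and a not-evaluable code for each measure on the reading form, with no additional X-ray or reader. The downside is that denominators will differ between the five measures and between time points.
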